10.1.4 Assessment of relationship of AE to treatment

Relationship of the AE to study drug will be classified as one of the following: not related, unlikely, possibly, probably, definitely. All AEs will be considered due to drug (AEs classified as unlikely, possibly, probably or definitely) unless clearly not related to therapy. The severity and seriousness of each AE will be assessed by the site investigators.

10.1.5 Follow-up of AEs

All AEs, including lab abnormalities that in the opinion of the investigator are clinically significant, will be followed until resolution, if possible. If an AE persists more than 30 days after the subject goes off study, the subject will be referred to their personal physician.

10.2 SERIOUS ADVERSE EVENTS (SAEs)

DEFINITION: ICH Guideline E2A and Fed. Reg. 62, Oct. 7, 1997 define SAEs as those events, occurring at any dose, which meet any of the following criteria:

- Results in death
- Is life threatening (*Note: the term life-threatening refers to an event in which the patient was at risk of death at the time of the event; it does not refer to an event which hypothetically might have caused death if it were more severe*).
- Requires inpatient hospitalization or prolongation of existing hospitalization
- Results in persistent or significant disability/incapacity
- Is a congenital abnormality/birth defect
- Events that may not meet these criteria, but which the investigator finds very unusual and/or potentially serious, will also be reported in the same manner.

Contact [name] by phone or e-mail within 24 hours of knowledge of the event. A SAE regardless of relatedness or expectedness will be reported to the Principal Investigator by telephone within 24 hours of the PI/study team becoming aware of the event.

FDA Notification by Sponsor: [name] will then notify the FDA by telephone or by facsimile transmission of any unexpected fatal or life-threatening experience associated with the use of the drug as soon as possible but no later than seven calendar days after the initial receipt of the information.

IRB Notification by Investigator: Reports of all SAEs (including follow-up information) will be submitted to the all IRBs per state and federal guidelines. Copies of each report and documentation of IRB notification and receipt will be kept in the Clinical Investigator's binder. AEs and/or laboratory abnormalities identified in the protocol as critical to safety evaluations will also be reported the IND sponsor.

MCC and all participating organizations will comply with applicable regulatory requirements at the participating institution related to reporting SAEs to the IRB.

Follow-up of SAE:

Site staff should send follow-up reports as requested when additional information is available or to resolve queries. Additional information should be entered on the SAE form in the appropriate format. Follow-up information should be sent to the Principal Investigator as soon as possible. SAEs will be followed until resolved or stable, especially for those related to the study agent.

11 STUDY MONITORING

11.1 Data Management

The Data Management team will consist of the PI, Biostatistician, and Data Entry Manager at MCC, Tampa, FL. As part of our efforts to ensure subject confidentiality, all names and other data, which might uniquely identify a subject, will be expunged from this data set. The database will be password protected and only the data entry person and project manager will have access to it. The computer that will house the database is part of a network that is backed up daily. The network also makes use of the latest in firewall technology to prevent unauthorized access or tampering and keeps up-to-date virus protection on each computer as well as the network.

Computer files will be backed on regular intervals. Informed consent documents will be kept in files in an area designated by the principal investigator.

The safety of the study will be monitored by the Principal Investigator according to the monitoring plan proposed in this Pilot clinical trial. The investigator will allocate adequate time for such monitoring activities. The investigator will also ensure that the monitor or other compliance or quality assurance reviewer is given access to all the above noted study-related documents and facilities (*e.g.*, pharmacy, diagnostic laboratory, *etc.*), and has adequate space to conduct the monitoring visit.

Internal Monitoring: Data will be captured in Oncore, Moffitt's Clinical Trial Database. The Case Report Forms will be reviewed by Moffitt's Internal Monitors, periodically throughout the conduct of this trial. The monitoring will include source data verification, utilizing research subject's medical records.

11.2 Case Report Forms

Participant data will be collected using protocol-specific case report forms (CRFs).

11.3 Source Documents

Original documents (*i.e.*, informed consent forms) will be treated as source documentation for this clinical trial.

11.4 Data and Safety Monitoring

Toxicities will be monitored continuously through the trial by the IRB, Moffitt and FDA. The PI and Biostatistician along with the MDs in the study will be responsible for reviewing AEs after 20 subjects have completed the study. If 50% of patients randomized to the treatment arm experience grade III or greater adverse events, we will discontinue this study.

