4.0 PARTICIPANT SELECTION

Women who have been diagnosed with stage I-III B breast cancer (BCa) and who have completed neoadjuvant or adjuvant treatment with anthracyclines and/or taxanes + or – Radiation therapy within the past 6 months (+/- 7 days) will be invited to be screened for eligibility to participate in this trial (subjects on concurrent endocrine therapy (TAM, Aromatase inhibitors are also eligible to participate as this is standard of care for this patient population). We will, in addition, expand our recruitment at the Moffitt Cancer Center to include the members of the Moffitt Cancer Center Affiliate Network (Total Cancer Care network consisting of 16 community hospital affiliates and 415 community oncologists statewide. With this additional network to recruit this patient population from, we are confident that we will be able to recruit the number of subjects needed for this study from each site. Based on the number of subjects that can be recruited from Moffitt, we conservatively estimate that we will recruit and retain 40 subjects during the 6 months recruitment period. Throughout the recruitment, data collection and retention period of this study we will focus on retaining high participation rates of an ethnically diverse population.

If women are already patients at Moffitt Cancer Center or one of its affiliates, they will be identified by one of the medical oncologists who are co-investigators in this trial based on the diagnosis and treatment received. Women who have been diagnosed with stage I-IIIB breast cancer (BCa) and who have completed neoadjuvant or adjuvant treatment with anthracyclines and/or taxanes + or – Radiation therapy within the past 6 months, (+/- 7 days) will be referred to the clinical research coordinator who will then invite these potentially eligible subjects to be screened for eligibility criteria to participate in this trial. All subjects referred to the research team from affiliate sites will be screened for eligibility. In this pilot clinical trial, all subjects, if identified as eligible based on initial screening in any other site other than the Moffitt Cancer center, will be required to come to the Moffitt cancer center if willing to continue to participate.

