5.7 Drug Storage of COGNUTRIN (VITABLUE and n-3 fatty acids): All investigational agents will be received, stored and dispensed by the Investigational pharmacy at MCC. Bottles with study agent will be stored at controlled room temperature (15-30 0 C).The PI, or a responsible party designated by the investigator, will maintain a careful record of receipt, disposition, and return of all study agent on the Investigational Agent Accountability Record. All study drug supplies will be kept in a locked limited access room. The study drug must not be used outside the context of the protocol. Under no circumstances will the investigator or .other site personnel supply study drug to other investigators, patients, or clinics, or allow supplies to be used other than directed by this protocol. Study agent may not be transferred from one patient to another, from one participating center to another participating center or from one protocol to another. All other transfers (i.e. patient or PI moves) must be approved in advance by the study PI. Every attempt will be made to collect all unused study agent supplies to be returned to the Moffitt Research Center PI office. The investigator will maintain records documenting the receipt, use, loss or other disposition of the investigational product, including batch or code numbers, and account for it's disposition on subject-by-subject basis, including specific dates and quantities. The source document, documenting the subject's participation in this clinical trial must be documented in the medical and research records. Destruction will be adequately documented.

5.8 Registration and Randomization: Potential subjects will be screened by the research coordinator using an Eligibility Checklist (Appendix I). The initial screening visit will verify patient eligibility to the study. A minimum of 40 subjects will be randomized to the pilot clinical trial. Within 6 months of completion of treatment with chemotherapy and radiation if applicable, we will screen the patients for cognitive function to determine the eligibility of participants to participate in the randomized trial portion of the study. If found eligible based on the criteria established for cognitive impairment, subjects will be ready for baseline data collection.

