7.3 Evaluations during Baseline/Randomization Visit

7.3.1 After eligibility has been confirmed based on screening tests using eligibility checklist, subjects will be randomized and supplied with a one-month supply of nutritional supplement (COGNUTRIN) or placebo (n=20/arm) and multivitamin .

7.3.2 Review of completed diet survey and concomitant medications.

7.3.3 Anthropometric measurements will be taken.

- 7.3.4 The following questionnaires will be completed: Godin-Leisure Time Exercise, Patient's Assessment of Own Functioning Inventory (PAOFI); Personal Health Questionnaire (PHQ-9), and Symptoms of Fatigue and Depression (FSI)
- 7.3.5 Cognitive testing will be administered (HVLТ-R: Form 1, COWA: T1, Color Trails Part 1& 2, Digit Span, SDMT, BVMT-R: Form 1, and Rey Complex Figure Copy)
- 7.3.6 Subjects will also undergo a structural and resting-state functional magnetic resonance Imaging (MRI/fMRI)

Subjects should not be randomized until eligibility has been confirmed. All components of eligibility will be confirmed (inclusion criteria and exclusion criteria).

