12.2 Sample Size/Accrual Rate

In this pilot trial, we plan to accrue 40 evaluable subjects. This is a feasibility clinical trial in preparation to inform the design of a well-powered randomized clinical trial.

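### The only scheduled safety review waits for 20 completers, which on the planned accrual falls at or just after the end of enrolment, and toxicity dropouts can delay it further

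*Combined protocol and SAP*

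**What the plan says.** Section 11.4 contains three statements on trial-level safety.

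- Oversight: "Toxicities will be monitored continuously through the trial by the IRB, Moffitt and FDA". No count, threshold or schedule is attached.
- One scheduled look, by the PI, the biostatistician and the study physicians: "reviewing AEs after 20 subjects have completed the study".
- One stopping criterion: "If 50% of patients randomized to the treatment arm experience grade III or greater adverse events, we will discontinue this study". It is not expressly confined to the scheduled look.

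On accrual, section 4.0 states "we conservatively estimate that we will recruit and retain 40 subjects during the 6 months recruitment period" and section 12.2 states "we plan to accrue 40 evaluable subjects". Section 5.8 sets 40 as the minimum number randomised, and section 7.3 allocates 20 to each arm. Section 4.3 expects 10% loss to follow-up.

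On time in the study, the schema places the end of intervention at week 12 or day 90 (plus or minus 7 days). Section 7.6 adds a telephone call 7 (plus or minus 3) days after stopping agent, after which the subject is off study.

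On leaving early, the action table in section 6.5 has agent discontinued for a grade 3 or 4 event, and an interruption of more than one week takes the subject out of the study. Section 8.4 lists finishing the intervention and follow-up as one reason for going off study and an AE or SAE as another.

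**The concern.** An interim safety review can do two things: stop treatment in subjects already on it, and stop further patients from being exposed. The second depends on the review coming while patients are still to be randomised. A trigger based on completers adds more than three months to the time needed to randomise 20 subjects, and here the whole planned accrual lasts only six months.

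The trigger also runs the wrong way. If subjects who leave because of toxicity do not count as having completed, more toxicity means slower progress to 20 and a later review. In addition, the 50% criterion needs counts by arm. Section 11.4 does not say who produces them, or who would apply the criterion before the scheduled look.

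**Working it through.** The plan gives neither a calendar time for the review nor operating characteristics for the rule, so there is no stated figure to reproduce. The check derives both.

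**Inputs.** Accrual rate 40/6 = 6.67 per month (section 4.0). Time to completion 84 + 7 = 91 days to 90 + 7 = 97 days (schema, section 7.6). Loss d = 0 or 10% (section 4.3). Accrual is assumed uniform, with 30.44 days per month.

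**Timing.** Month of the review = [20/(1 − d)]/6.67 + days/30.44. Number randomised by then = min(40, 6.67 × month).

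| Days to completion | Loss | Month of 20th completion | Randomised, of 40 |
|---|---|---|---|
| 91 | 0 | 3.00 + 2.99 = 5.99 | 39.9 |
| 97 | 0 | 3.00 + 3.19 = 6.19 | 40 |
| 91 | 10% | 3.33 + 2.99 = 6.32 | 40 |
| 97 | 10% | 3.33 + 3.19 = 6.52 | 40 |

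Planned accrual ends at month 6.0.

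**Sensitivity.**
- The extremes of the visit windows give month 5.66 (81 days, no loss, 37.7 randomised) to month 6.85 (107 days, 10% loss, all 40).
- If completion means only the end-of-treatment visit (84 to 90 days, no loss), the review falls at month 5.76 to 5.96, with 38.4 to 39.7 randomised.
- If 40/0.9 = 44.4 are recruited in six months so that 40 are retained, it falls at month 5.99 to 6.19, with essentially all 44.4 in.
- In 100,000 simulated trials per setting, with random arrivals and 91 to 97 days, all 40 are already randomised in 56% to 71% of trials without loss and in 77% to 87% with 10% loss. The median is 40 and the 5th percentile 35 to 38.
- Slower accrual (assumed): over 12 months, 30 to 33 of 40 are randomised at the review; over 18 months, 27 to 29. The review precedes full accrual once accrual exceeds about 6.0 to 6.4 months without loss, or 6.7 to 7.2 months with 10% loss.

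**What a stop could still do.** At the 20th completion on planned accrual, 40 − 20 = 20 subjects have not completed if none are lost. With 10% loss, 40 − 22.2 = 17.8 were randomised too late to have completed, of whom about 17.8 × 0.9 = 16 are retained.

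**Delay from toxicity.** Suppose the active arm reaches the rule's own 50%, those subjects do not count as completers, and nobody else is lost. Then 0.5 × 0.5 + 0.5 × 1 = 75% complete, 20/0.75 = 26.7 must be randomised, and the review moves to 26.7/6.67 + 2.99 to 3.19 = month 7.0 to 7.2.

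**The 50% criterion.** Its denominator is those randomised to the treatment arm. With the full 20, at least 10 must have a grade 3 or higher event. Binomial P(X ≥ 10 | n = 20) is 0.048, 0.245 and 0.588 at true rates of 30%, 40% and 50%. These assume full follow-up in all 20, which subjects randomised last would not have at the review.

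**Illustrative alternative.** A review when the first 20 randomised reach week 4 falls at 3.00 + 28/30.44 = month 3.92, with 6.67 × 3.92 = 26 randomised and 14 still to come. About 13 would then be in the active arm. Half of those randomised so far means 7 of 13, while half of the full arm still means 10, so the denominator has to be stated.

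**The case against.** A reader might infer that subjects who stop because of toxicity are left out of the safety rule. The documents do not support that. The criterion covers everyone randomised to the treatment arm, nothing in section 11.4 limits the events reviewed to completers, and section 10.1.1 records all events after the start of agent. What stands is narrower: such subjects probably do not advance the trigger. Even that is a reading, because off agent (section 8.3) and off study (section 8.4) are separate, treated subjects are asked for post-intervention procedures where feasible, and the call in section 7.6 is timed from stopping agent. An early stopper could therefore be counted sooner, or not at all. Since section 8.4 separates completion from an AE or SAE, not at all is the more natural reading, but the text leaves it open.

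A reader might also infer that the review cannot limit enrolment. That goes too far. The timing is close to a tie with the end of accrual, and it rests on the six-month plan. The May 2014 amendment letter reports over 90 screened in 30 days with none eligible, and recruitment terms were still being amended in October 2015. This suggests slower accrual, although no enrolment counts are given and the eligibility criteria changed.

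Other safeguards exist: discontinuation and PI notification for grade 3 or 4 events (section 6.5), AE log sign-off at months 1 and 2 (section 7.7.8), SAE notice within 24 hours (section 10.2), monthly laboratory tests, and the continuous oversight in section 11.4. They matter for individual subjects, but none is described as producing the by-arm count that the 50% criterion needs.

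Finally, it is tempting to assess the rule on the 10 or so active subjects among the 20 completers. The stated denominator is subjects randomised, so that calculation does not describe this rule.

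**Conclusion.** The point holds in a limited form. On the plan's own accrual, treatment time and loss, the only scheduled review falls at about month 6.0 to 6.5, against accrual ending at month 6.0. It can then protect few or no patients from being randomised, though it could still stop treatment in roughly 16 to 20 subjects who have not finished. The conclusion assumes uniform accrual of 40 in six months, and it weakens as accrual slows.

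The toxicity delay is conditional on early leavers not counting as completers. In the example at the rule's own 50% rate, it adds 20/0.75 − 20 = 6.7 subjects, or about one month.

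Unblinding of the PI is a risk and not something the plan states. The PI is a named reviewer and signs AE logs, but section 11.4 does not say that the PI receives counts by arm. The gap is that it does not say who does.

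**What to change.** Reconcile section 11.4 with sections 4.0, 6.5 and 8.4, keeping the sponsor's 50% threshold.

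- Base the scheduled review on subjects randomised, or started on agent, and not on subjects completed. The sponsor would time it to an existing monthly safety visit. The week-4 calculation shows what such a change could gain and is not a recommended look. An earlier review also has less follow-up per subject, which the sponsor should weigh.
- If a completer trigger is kept, define completion and say whether subjects who stop early for toxicity count.
- State whether the denominator is those randomised to the treatment arm so far or the full 20, and report the trigger probabilities for the choice made (5%, 25% and 59% at true rates of 30%, 40% and 50% for 10 of 20).
- Say who applies the criterion before the scheduled review, and how the continuous oversight obtains counts by arm.
- Have the biostatistician prepare the by-arm counts, so that the PI who signs AE logs can remain blinded.

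The cost is protocol wording and one short tabulation of AE data already collected at the monthly visits.

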11.5 Sponsor or FDA Monitoring

The investigator will permit study-related monitoring, auditing, and inspection by the IRB and government regulatory bodies (FDA) of all study-related documents (*e.g.*, source documents, regulatory documents, laboratory data, data collection instruments, *etc.*).

11.6 Record Retention

Records for all participants will be retained, at a minimum, for two years after the approval of a New Drug Application (NDA) or as otherwise, directed by the Sponsor. The sponsor will be notified prior to the planned destruction of any materials. The records should be accessible for inspection and copying by authorized persons of the Food and Drug Administration.

12 STATISTICAL CONSIDERATIONS

12.1 Study Design/Endpoints

The central hypothesis for this Pilot clinical trial is that adults who receive COGNUTRIN will exhibit reduction in the number of impaired cognitive tests, as compared to adults on the placebo.

12.2 Sample Size/Accrual Rate

In this pilot trial, we plan to accrue 40 evaluable subjects. This is a feasibility clinical trial in preparation to inform the design of a well-powered randomized clinical trial.

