(a) Within 6 months of completing neoadjuvant or adjuvant treatment with anthracyclines and/or taxanes + or – radiation therapy (subjects on concurrent endocrine therapy (TAM, Aromatase inhibitors are also eligible to participate as this is standard of care for this patient population); (b) No evidence of dementia (MMSE \geq 23) but some evidence of cognitive impairment (each subject will be required to answer in the affirmative: ‘do you have problems with memory and attention since having chemotherapy, and do you believe chemotherapy contributed to the problems?’); (c) Collect blood for CBC/CMP/PT/PTT, LDL and antioxidant and biomarkers of inflammation; (d) Conduct Mini-Mental Status Exam

If yes-

Baseline/Randomization (In person):

(a) Confirm eligibility based on screening tests; (b) Obtain baseline food records; (c) Complete Demographic and Godin Leisure-Time Exercise Questionnaires; (d) Conduct battery of cognitive tests including Weschler Test of Adult Reading, Hopkins Verbal Learning Test, Revised (Form 1), COWA (T1), Color Trails, Part 1 & 2, Digit Span (Subset of WMS-IV), Symbol Digit Modalities Test, Brief Visuospatial Memory Test-Revised (Form 1), and Rey Complex Figure Copy; (e) Patient’s Assessment of Own Functioning Inventory (PAOFI); (f) Structural and resting-state functional magnetic resonance imaging (MRI/fMRI); (g) Complete questionnaires for symptoms of fatigue and depression (PHQ-9 and FSI); (h) Randomize and supply participant with one-month supply of nutritional supplement (COGNUTRIN) or placebo (n=20/arm), multivitamin, and study agent intake and symptom logs

Intervention:

One of 2 arms, self-administration of nutritional supplement (COGNUTRIN) or placebo for 3 months plus multivitamin

Weeks 3, 7, & 11:

Remind patient to complete diet records and schedule monthly visits

Weeks 4 & 8 (+/- 7 days) (In person):

(a) Collect blood for CBC, CMP, PT/PTT; (b) Collect unused nutritional supplement/ placebo, multivitamin, and completed study agent intake and symptom log form; (c) Collect completed diet survey; (d) Supply participant with new one-month supply of nutritional supplement or placebo and study agent intake and symptom logs

Week 12, 3 months or 90 days (+/- 7 days): End of Intervention (In person):

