Our criteria for inclusion of subjects in this trial is that subjects recruited are able to understand and sign the informed consent. The subjects must also be fluent English-speaking (Persons who are not fluent English speakers are excluded from the current proposal because many of the cognitive tests that are administered are language-based and are heavily influenced by first language). Subjects must also have no evidence of dementia (MMSE \geq 23) but some evidence of cognitive impairment (each subject will be required to answer in the affirmative: ‘do you have problems with memory and attention since having chemotherapy, and do you believe chemotherapy contributed to the problems?’). Each subject must be aware of the nature of his current medical condition and must be willing to give consent after being informed of the experimental nature of therapy, alternatives, potential benefits, side-effects, risks and discomforts. If a subject is determined to be cognitively impaired to the point of not meeting the above criteria at screening by the investigative team, they will not be included in this pilot phase of the clinical trial, making the use of proxy’s unnecessary.

4.3 Anticipated problems with subject recruitment and retention: Our group has extensive experience conducting research with breast cancer patients as well as studies collecting neuropsychological data, questionnaires, blood samples, and MRI/fMRI. Thus, we expect difficulties to be minimal. As with all clinical trials, we anticipate that there will a 10% loss of subjects to follow up, although, in our experience, breast cancer survivors tend to be a highly motivated group and the time between assessments is short and subjects will be required to come in monthly for monitoring safety and compliance. Moffitt Cancer center, as the only NCI designated Comprehensive cancer center in the State of Florida has a substantial number of subjects treated for breast cancer.

The recruitment, intervention and retention team (PI, [name], Co-I [name] and CRC) will initiate, develop and implement procedures to deal with and solve problems with attrition. As we have with our previous and current intervention trials, we will take measures to ensure that loss to follow-up is minimal, implementing several strategies for recruitment and retention as follows:

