12.4 Primary Endpoint

The primary efficacy endpoint is to generate effect sizes for changes in the number of impaired neuropsychological tests. The planned intervention period is three months. Neuropsychological outcomes will be examined using a 2 (group; COGNUTRIN, placebo) X 2 (time; baseline, three-months) repeated measures ANOVA to examine differences in the number of impaired neuropsychological tests. Age, premorbid cognitive functioning, depression and fatigue will be evaluated for association with neurocognitive performance and entered as covariates in statistical analyses if a marginally significant association ($p < .10$) is observed.

The primary efficacy endpoint is to generate effect sizes for changes in the number of impaired neuropsychological tests. The planned intervention period is three months. Neuropsychological outcomes will be examined using a 2 (group; COGNUTRIN, placebo) X 2 (time; baseline, three-months) repeated measures ANOVA to examine differences in the number of impaired neuropsychological tests. Age, premorbid cognitive functioning, depression and fatigue will be evaluated for association with neurocognitive performance and entered as covariates in statistical analyses if a marginally significant association ($p < .10$) is observed. The sample size of 20 patients per arm will allow us to generate useful information for future studies, in terms of anticipated effect size. Although this pilot study is not designed to be fully powered, the current sample size will allow us to detect an effect size difference of .40 for a one-tailed paired sample t-test, on account of the matched groups, at power of .80 and an alpha of .05. Moreover, the sample sizes will enable us to detect a group X time interaction of .23, with an alpha of .05, power of .80, and a stability coefficient of .5.

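### Section 12.4 claims 80% power for an effect of .40 from a paired test that this two-arm design does not support; separately, the randomised and evaluable numbers are not reconciled

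*Combined protocol and SAP*

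**What the plan says.** Section 12.4 opens its power statement with "The sample size of 20 patients per arm will allow us to generate useful information for future studies". It adds that the pilot is not designed to be fully powered, and then gives two specific claims, both at alpha .05 and power .80:

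- an effect size of .40, by a one-tailed paired t-test, justified by the groups being matched;
- an interaction: "the sample sizes will enable us to detect a group X time interaction of .23", with a stability coefficient of .5.

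The hypothesis in section 12.1 compares COGNUTRIN with placebo. Section 12.3 describes block randomisation that balances the arms on radiation and concurrent endocrine therapy.

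On numbers:

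- Section 12.2: "we plan to accrue 40 evaluable subjects".
- Schema: "nutritional supplement (COGNUTRIN) or placebo (n=20/arm" at randomisation. Section 7.3 says the same.
- Section 5.8: "A minimum of 40 subjects will be randomized to the pilot clinical trial".
- Section 4.0: "we conservatively estimate that we will recruit and retain 40 subjects during the 6 months recruitment period".
- Section 4.3: "we anticipate that there will a 10% loss of subjects to follow up".

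No inflated randomisation number and no replacement rule is given.

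**The concern.** A paired t-test needs pairs. Patients in two randomised arms are independent unless they were matched individually, and balancing arms on two treatment factors does not pair one patient with another. If the test is paired within person (baseline against three months), it measures change in one group and does not compare COGNUTRIN with placebo. Either way the .40 does not describe what this trial can detect between arms.

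The trial exists to inform a well-powered successor. Someone planning that trial could take .40 as an effect that 20 per arm can detect, when the between-arm figure is more than twice as large.

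The second, smaller concern is that 20 per arm at randomisation, 10% loss and 40 evaluable cannot all be exact. The site cannot tell from the text whether to stop randomising at 40.

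**Working it through.** **Inputs.** d = .40, one-tailed, alpha .05; interaction .23, alpha .05, correlation .5; 20 per arm (all section 12.4). Loss 10% (section 4.3). Evaluable target 40 (section 12.2). Assumptions: .23 is Cohen's f, which section 12.4 does not say; loss falls equally on both arms; missing outcomes are not imputed.

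**1. Reproducing the .40 claim.** Paired t-test, one-tailed, noncentral t with df = n − 1 and noncentrality d√n.

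- n = 40 pairs: noncentrality .40 × √40 = 2.53, df 39, power 0.800. This matches the plan.
- n = 20 pairs: noncentrality .40 × √20 = 1.79, df 19, power 0.532. The effect detectable at 80% is d = 0.58.

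The claim therefore needs all 40 patients treated as 40 pairs in one group. Matching across arms yields at most 20 pairs, and a before-after test within one arm also has 20.

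**2. The comparison the design provides.** Two-sample t-test, 20 per arm, df = 38, noncentrality d√(n/2).

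- d = .40, one-tailed: noncentrality .40 × √10 = 1.26, power 0.344. The effect detectable at 80% is d = 0.80.
- Two-sided, the effect detectable at 80% is d = 0.91.

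**3. Reproducing the interaction claim.** Noncentral F with 1 and N − 2 df, λ = f² × N × 2/(1 − .5) = 4f²N.

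- N = 40, f = .23: λ = 4 × .0529 × 40 = 8.46, power 0.809. This is consistent with the stated .80. The f detectable at 80% is .227.

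With two time points this test is the two-sided two-sample t-test on change, for which λ = (N/4)δ², with δ in SDs of change. Setting the two equal gives δ = 4f. So f = .227 is 0.91 SD, in agreement with step 2, and the plan's own .23 is 4 × .23 = 0.92 SD. Section 12.4 thus gives .40 in one sentence and the equivalent of 0.92 SD in the next, and only the second concerns a difference between arms.

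**4. The effect of loss, if randomisation stops at 40.** 40 × 0.90 = 36 analysed.

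- N = 36, f = .23: λ = 4 × .0529 × 36 = 7.62, power 0.765. The detectable f is .240, and 4 × .2403 = 0.96 SD.
- Under independent 10% loss, the chance that all 40 of 40 are evaluable is 0.9⁴⁰ = 1.5%.
- To expect 40 evaluable: 40/0.9 = 44.4, so 45, or 46 for equal arms (23 each).

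**The case against.** The protocol does not present itself as adequately powered. Sections 8.1 and 8.2 say the sample size will not give sufficient power, and section 12.4 repeats the caution. Section 12.2 gives feasibility as the purpose, and section 12.4 adds effect-size estimation. All of this stands, so a reader should not infer that the power statement is the only reason given for 20 per arm. But the caution does not make a specific figure correct: section 12.4 still attaches 80% power to .40.

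On the numbers, a reader might infer that the plan cannot deliver 40 evaluable patients, so that both power figures are overstated because of dropout. The documents do not support that. Section 5.8 sets 40 as a minimum to randomise, and section 4.0 speaks of recruiting and retaining 40. Sections 7.7.13 and 9.1 ship specimens once 40 patients have samples from before and after the intervention. These allow more than 40 to be randomised, and section 12.4 does not say whether its 20 per arm is randomised or analysed. If 40 are analysed, the .23 figure holds. Nor is dropout what undermines the .40: going from 40 to 36 pairs lowers its power only from 0.80 to 0.76, whereas the choice of test takes it to 0.53 or 0.34.

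It could also be said that matching refers to the balanced randomisation in section 12.3. That is balance between groups, and it does not create pairs for a paired test.

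**Conclusion.** Wrong as written. The claim of 80% power for .40 holds only for 40 pairs analysed as one group, which is not the trial's comparison. With 20 pairs the power is 53%, and with 20 versus 20 independent patients, one-tailed, it is 34%. This conclusion does not depend on how many patients are lost.

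The numbers issue is secondary. The documents do not reconcile 40 evaluable, 20 per arm at randomisation and 10% loss. If randomisation stops at 40, power for the .23 interaction is 76.5% against the stated 80%, and the detectable f moves from .227 to .240. If enough are randomised to leave 40 analysed, there is no loss. The interaction figures rest on reading .23 as Cohen's f with correlation .5, a reading that the close match at 40 supports but the text does not confirm. They also assume equal loss in both arms and no imputation.

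**What to change.** In section 12.4, delete the one-tailed paired-test sentence. State instead the two-sided between-arm difference in change detectable at 80% power for the number analysed: about 0.91 SD (f = .227) with 40, or about 0.96 SD (f = .240) with 36. Name .23 as Cohen's f if that is what was meant.

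In sections 12.2, 5.8 and 7.3, say whether 40 is the randomised or the evaluable number:

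- If 40 are randomised, state about 36 evaluable, use the 36-patient figure, and bring the specimen-shipping condition in sections 7.7.13 and 9.1 into line.
- If 40 evaluable is the existing target, the matching randomised number under the protocol's own 10% loss is 46 (23 per arm).

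Which of the two was intended is for the sponsor to state.

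The section 12.4 change costs only wording, and the stated detectable effect becomes less favourable. Clarifying to 46 means six more randomised patients than 40; clarifying to 36 evaluable lowers the target in section 12.2.
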